6.2 Secondary Endpoints

Functional trajectories and resiliency will be evaluated using generalized linear mixed models (GLMMS). This model allows for the estimation of intercept and slopes at both the individual and sample level. GLMMs can determine whether factors affect all patient trajectories in similar ways or whether they affect individual trajectories differently. To allow for possible changes in functional status over time (e.g., a change-point analysis) the ‘segmented’ package in R will be used.^{43,44} Participants’ functional status scores will be modeled using a segmented mixed model with random change points. Estimating the change point identifies the point in time that patients’ functional status scores change during the 12-months post-diagnosis. We anticipate that the start of treatment will be a change point depending on treatment tolerability vs. toxicity. This model allows for random and fixed effects, permitting analysis of between-subject and within-subject variance in longitudinal observations.

Resiliency will be defined as the ability to maintain or regain at least 50% of baseline functional status at any point during the 12 months after diagnosis with specific emphasis at 3 and 6-months post- the start of treatment. The association between resiliency and clinical factors will be evaluated with appropriate statistical techniques for the specific measure (e.g. Chi-square tests will compare categorical variables between participants demonstrating resiliency vs. worsening functional status; a two-sample t-test or Wilcoxon Rank Sum test will compare continuous variables). We will characterize differences in resiliency within each of these pre-defined groups. GLMMs will test for differences in resiliency between these groups. Models will be adjusted for important clinical and demographic variables. The data obtained from the primary endpoint will be used to refine the timing and duration of the pilot intervention as described in our secondary endpoint. Using GLMMS we will compare functional status in the 24-week follow-up period using both functional status measurement strategies to inform the survey design of a larger intervention trial.

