3.0 METHODS

3.1 Study Overview

This is a prospective, longitudinal study of 20 adults ≥ 60 years of age with advanced thoracic malignancy (NSCLC or SCLC) who plan to receive either immunotherapy and or chemotherapy treatment from the OSUCCC Thoracic Oncology clinic. This cohort is a 12-week pilot intervention consisting of a physical therapy and progressive muscle relaxation program delivered to older adults with advanced lung cancer. Functional trajectories and resiliency will be characterized in this cohort. Enrolled patients will participate in in-person physical therapy and progressive muscle relaxation sessions that are incorporated into routine treatment visits as well as performed via virtual health on the non-treatment weeks. Patients’ functional status will be assessed every 3 weeks and clinical outcomes will be evaluated every 6 weeks. Correlative biomarkers will also be assessed through blood and stool sample collection. Patient follow up will continue through 24 months post enrollment for 1 year and 2 year overall survival.

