4.6 Functional Status Assessments

The Functional Status Assessment survey [APPENDIX G] will be assessed every 3 weeks by the CRC either in person, by phone, by email, or through virtual health monitoring. These surveys will be comprised of 16 activities including seven Activities of Daily Living (ADL) measures⁷, 5 Instrumental Activities of Daily Living (IADL) measures²⁵, and 3 mobility activities.⁹ For each activity, disability is defined as the need for personal assistance or inability to perform the activity. Activities are scored as 0 being no help, 1 being with help, and 2 meaning unable to perform the activity. Higher scores indicate greater disability or a lower functional status. The ADL trajectories will include; eating, grooming, bathing, dressing, walking, toileting, and transferring, the IADL trajectories include; shopping, housework, meal preparation, taking medications, and managing finances, and the mobility measures will include; walking a quarter mile, climbing a flight of stairs, or lifting/carrying a 10lbs. The final mobility activity included is if the participant drove a car in the past month, where disability is defined as having not driven. In addition to these 16 measures, the patients will undergo the EQ-5D-5L [APPENDIX H]. The EQ-5D-5L²⁶ is a brief 5 question assessment that captures disability in self-care, mobility, and usual activities. It uses a scoring scale from 3, meaning no disability to 15 points, indicating severe disability. This tool has been mapped to the EORTC-QLQ-C30,²⁷ specifically in patients with advanced NSCLC²⁸. However, the EQ-5D-5L has been shown to be the preferred assessment due to its shortened length and its improved sensitivity and face validity.²⁶

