6.0 STATISTICAL ANALYSIS

6.1 Primary Endpoint

In order to evaluate the feasibility of the pilot intervention we will determine, recruitment, adherence, and retention rates at 12-weeks of follow-up. Follow-up will continue through 24 weeks post-enrollment. Recruitment rates will be defined as the proportion of screened older adults accrued relative to those approached in the OSUCCC Thoracic Oncology Clinic.

Successful recruitment rates will be defined as $\geq 50\%$ of older adults (≥ 60 years) approached agree to participate. Study adherence will be defined as the completion of $\geq 70\%$ of the program sessions, repeated assessments, and collection of bio specimens either at the end of the study period or death, whichever occurs first. Retention rates will be defined as the percentage of participants not lost to follow-up at 6, 12, and 24 weeks post-enrollment. Death during active follow-up will not be considered as lost to follow-up. We are excluding those people who die because our population of interest is those who live long enough to benefit from this intervention. We will enroll 30 participants to account for a conservative drop out of 30% for a projected sample size of 20 participants who survive a 6 – month period. Reasons for missing any scheduled collection dates will be documented, and the proportions of missing information at each time point will be calculated.

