#A3802) and random hexamer primers (Invitrogen #588875) as directed by the manufacturers. p16 levels will be measured using a Taqman-based quantitative RT-PCR methods essentially as described by Liu et al. (20). Validated Taqman-based controls for T-cell purity (CD3G, Applied Biosystems #4331182 Hs00962186), sample viability (p14ARF, Applied Biosystems #4351370 HUMP14-ARF3) and RNA quantity (YWHAZ, Applied Biosystems #4331182 Hs03044281) are included in this analysis. Data clean up: Data will be filtered to exclude relatively invariant features (IQR = 0.5) and features below the detection threshold (defined for each sample by a cutoff corresponding to approximately twice standard deviation of negative control probes plus the mean of them) in at least half of the samples. Basic analysis Using R/Bioconductor and the filtered dataset, linear models for microarray data analysis⁴⁷ will be employed with a contrast matrix for the comparisons. P values will be used to rank miRNAs and mRNA of interest, and correction for multiple comparisons will be done by the Benjamini-Hochberg method.⁴⁸

Assessment*:	Screen	Visit 1 (Baseline)	Every Treatment Visit	Visit 2 (4 weeks)	Visit 3 (7 weeks)	Visit 4 (10 weeks)	Visit 5 (13 Weeks) End of intervention	Visit 6 (24 weeks)	Follow up to 24 months (2 years)
Signed Informed Consent	x								
Inclusion/Exclusion	x								
Medical & Cancer History	x								
Sociodemographic		x							
Disease Assessments		x						x	
Physical Exam		x			x		x	x	
Vital Signs		x			x		x	x	
SPPB		x			x		x	x	
2-6 MWT		x			x		x	x	
PROMIS-10		x			x		x	x	
Blood Chemistry		x			x		x	x	
Biomarker Testing (blood and stool)		x			x		x	x	
Functional Status Assessments		x	x	x	x	x	x	x	
PROMIS-10		x		x	x	x	x	x	
GAD-7		x		x	x	x	x	x	
PHQ-9		x		x	x	x	x	x	
EORTCQLQ-30		x		x	x	x	x	x	
EORTC LC-13		x		x	x	x	x	x	
POMS-12		x	x	x	x	x	x	x	

Toxicities/ Disease Response		X		X	X	X	X	X	
Survival Status									X
Semi-structured interview							X		

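### Section 6.2 reads an estimated change point as the time function changes, but patient-level change points are unlikely to be well identified and nothing checks that a change exists

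*Combined protocol and SAP*

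**What the plan says.** Section 6.2 opens with generalized linear mixed models that estimate intercepts and slopes for individuals and for the sample. It then adds a change-point analysis: the segmented "package in R will be used", and "functional status scores will be modeled using a segmented mixed model with random change points". The interpretation is stated outright: "Estimating the change point identifies the point in time" at which scores change in the 12 months after diagnosis, and treatment start is expected to be such a point. The section gives no test for the existence of a change, random-effect structure, convergence rule, minimum number of scores or fallback.

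On the amount of data, the plan speaks in several places:

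- **Patients.** Section 3.1: "This is a prospective, longitudinal study of 20 adults". Section 6.1: "We will enroll 30 participants to account for a conservative drop out of 30% for a projected sample size of 20 participants".
- **Scores, text.** Section 4.6: "The Functional Status Assessment survey [APPENDIX G] will be assessed every 3 weeks by the CRC". Section 4.1 adds assessments triggered by events, including worsening function.
- **Scores, calendar.** In the Study Calendar (8.0) the row "Functional Status Assessments" is marked at six dated visits (baseline and weeks 4, 7, 10, 13 and 24) and also at every treatment visit, with no number given.
- **Entry.** Section 3.3 admits patients at any point in their treatment.

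**The concern.** A random change point asks each patient's few scores to show when that patient's slope bends. If they carry little information on this, the fit may stop with an error, may shrink the between-patient spread to zero so that everyone shares one time, or may place a bend in a trajectory that is steady. Under 6.2 as worded, whatever the fit returns is read as a real time of functional change. At stake is a secondary result on functional trajectories, in a section whose functional-status modelling is meant to inform a larger trial. A reported change point that is an artefact of fitting could mislead that design.

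**Working it through.** **1. The plan's own sizing.** Section 6.2.1 sizes the study on the follow-up rate only: 40% against 64%, one-sided 10%, 80% power. Normal approximation: n = [1.282√(0.4×0.6) + 0.842√(0.64×0.36)]² / 0.24² = 18.5, so 19; power at n = 20 is 82.3%. This agrees with 20 patients. No precision or power is stated for the change-point model, so there is nothing further to reproduce.

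**2. Data available.**
- Six dated scores in 20 patients: 20 × 6 = 120.
- Every 3 weeks to week 24: 24/3 + 1 = 9 scores.
- Dated visits plus assumed 3-weekly treatment visits: 6 + 9 − 2 shared (baseline, week 24) = 13 scores. In 30 patients: 390.
- Parameters if intercept, slope, bend and change point all vary by patient: 4 fixed effects + 4 variances + 1 residual = 9, or 4 + 10 + 1 = 15 with unstructured covariance.

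**3. Information in one patient's scores.** Suppose a patient's intercept, slope and bend δ were known. Each score after the change point moves by δ for each week the change point moves, so k later scores with residual SD σ give SE = σ/(δ√k). With a change at week 10, two dated scores follow (weeks 13 and 24). Take a between-patient SD of 3 weeks (assumed).
- δ = 0.25 points/week, σ = 1.5: SE = 1.5/(0.25 × 1.414) = 4.2 weeks. Share of variance explained = 9/(9 + 18) = 33%.
- δ = 0.5, σ = 1.0: SE = 1.0/(0.5 × 1.414) = 1.4 weeks. Share = 9/(9 + 2) = 82%.

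These are optimistic. With only the population parameters known, six scores explained 9-45% for σ of 1-2 and δ of 0.2-0.4 (between-patient SD 4 weeks). A second check with other inputs gave 6-59%.

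**4. Simulation, exact maximum likelihood (100 data sets per row).** Assumed: Gaussian scores, no missing data, baseline mean 6, between-patient SD 2.5, slope SD 0.08/week; where there is a bend, its mean is week 10 and its SD 3 weeks.

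| Bend/week, residual SD | Patients, scores | Change-point SD put at about zero | Mean change point, 5-95% (weeks) |
|---|---|---|---|
| 0.25, 1.5 | 20, 6 | 38% | 2.4-16.2 |
| 0.25, 1.5 | 20, 13 | 34% | 5.0-14.8 |
| 0.25, 1.5 | 30, 13 | 21% | 7.0-14.4 |
| 0.5, 1.0 | 20, 6 | 13% | 8.2-12.6 |

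**5. No true change (20 patients, residual SD 1.5).** With 6 scores, 89% of fits placed the mean change point inside the observed period; the bend was nominally significant in 22% (likelihood ratio against chi-square on 1 df) to 27% (Wald). With 13 scores: 94%, and 25% to 28%. A simpler model with one common change point gave 12.6% by Wald in 1000 runs. A further simulation over 6 or 9 scores and 20 or 30 patients gave 11-18%. When the likelihood ratio was referred to 3 df (bend, mean change point and its SD), rejection fell to 3% and 4%.

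**6. The named R package (segmented 2.1.4, diagonal random effects, 20 patients, 6 scores, 40 data sets per setting).** Errors stopped 65% of fits with no bend, 17% at bend 0.25 and none at bend 0.5 with residual SD 1.0. The change-point SD came out below 0.3 weeks (true 3) in 67% and 45% of fits at the two bends. At the stronger bend the mean was recovered (5-95%: weeks 8.6-11.7). With 13 scores and bend 0.25, none failed but 65% still fell below 0.3 weeks.

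**7. Timing.** For a patient enrolled on treatment, treatment start lies at or before week 0, so no score precedes the expected change point. Dated scores span 24 of 52 weeks (46%) of any 12-month window. A patient enrolled at diagnosis is followed for under half of it. For dated scores to reach 12 months, enrollment must fall at least 52 − 24 = 28 weeks after diagnosis, and those first weeks are then unobserved.

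**The case against.** A reader might infer that the model cannot be supported at all. The documents and figures do not show that: with a strong shared bend and low noise it fits, and the average change point is recovered. The weak part is the patient-to-patient spread.

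A reader might also take six scores in 20 patients as the ceiling. It is only the dated minimum. The 3-weekly text, the treatment-visit column and the triggered scores add data, and a mixed model uses partial data from all 30 enrolled. More data reduce the problem without removing it (21% collapse with 30 patients and 13 scores). Triggered scores are prompted partly by worsening function, so their timing depends on the outcome.

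Nor would every steady trajectory be reported as bending: many such fits stop with an error, and most that converge are not nominally significant. The error and collapse rates depend on one fitting set-up and on inputs the plan does not give.

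Three further points stand. Section 6.2 already names a model with individual intercepts and slopes, so a failed segmented fit leaves a trajectory analysis, although no rule says which result is reported. The documents do not say how many patients will already be on treatment; if none are, the treatment-start problem does not arise. The endpoint is secondary, and no feasibility decision uses it.

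**Conclusion.** The point holds as a problem of identification and interpretation. Patient-level change points are unlikely to be well identified with 20 to 30 patients and 6 to 13 scores each, unless the bend is large and the noise low. Section 6.2 nevertheless reads the estimate as the time of change, without checking that one exists. Under the assumed inputs, a naive test of the bend is wrong in roughly 11-28% of no-change data sets instead of 5%. Entry during treatment and dated scores ending at week 24 weaken the stated target further.

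The rates rest on assumed variances and bends, and the simulations in steps 4 to 6 on complete Gaussian data, which is favourable for a bounded score of about 0-32 (16 items × 2). Monte Carlo error is up to about 5 points for the maximum-likelihood results in steps 4 and 5 and 8 for the R package. The direction is the same across set-ups; the exact percentages should not be relied on. The primary feasibility conclusion is unaffected.

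**What to change.** Rewrite the change-point paragraph of 6.2:

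- Make the mixed model with random intercept and slope the main trajectory analysis. Allow a slope change at treatment start only for patients with scores before it.
- Do not add a fixed bend at week 13 as a substitute: only one dated score follows it.
- Label any estimated change point exploratory and make it common to all patients. Report it only if it beats the no-change model on a criterion stated in advance, such as BIC or a bootstrap or Davies-type test, with an interval from resampling patients.
- State what is reported if the fit fails.
- Replace the sentence that treats the estimate as identifying the time of change, and restate the period that the scores can cover.

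The cost is about a paragraph of text and no new data. What is lost is patient-specific change times, which these data are unlikely to deliver. The existence check need not cost much: in step 4's simulations, the 3-df comparison still detected a bend of 0.25 in 87% (20 patients, 6 scores) to 100% (30 patients, 13 scores) of data sets.

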3.3 Inclusion Criteria

- Age ≥ 60
- Diagnosed with advanced lung cancer: unresectable stage IIIA, IIIB, or stage IV NSCLC or extensive stage SCLC
- Intent to receive treatment from the OSUCCC Thoracic Oncology Clinic
- Patients are eligible at any time point during their treatment here at OSU. Rationale for this timeframe is due to the overwhelming nature of the first few visits and uncertainty

around an eventual treatment plan. Patients at any stage of their treatment can participate and benefit from a physical therapy and psychosocial intervention. Patients will be approached at their initial visit but we can also offer enrollment at any one of the patients regularly scheduled clinic visits. .

- Ability to understand and willingness to sign an informed consent document (or indicate approval or disapproval by another means).

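### Resiliency can be met at any single visit in a window that does not fit enrolment; classify it at fixed study visits instead

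*Combined protocol and SAP*

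**What the plan says.** Section 6.2 of the combined protocol and SAP treats a patient as resilient for being able to "maintain or regain at least 50% of baseline functional status at any point during the 12 months after diagnosis". The only qualification is a remark on timing, that this is to be read "with specific emphasis at 3 and 6-months post- the start of treatment". Clinical factors are then compared between "participants demonstrating resiliency vs. worsening functional status", using chi-square tests for categorical factors and t or Wilcoxon tests for continuous ones. The section adds that "GLMMs will test for differences in resiliency between these groups". It also sets the change-point analysis of functional scores over the year following diagnosis and expects treatment start to be a change point.

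Section 4.6 describes two surveys. The 16-item survey scores each activity 0, 1 or 2, and "Higher scores indicate greater disability or a lower functional status". The EQ-5D-5L runs from 3 to 15, also with higher as worse. Driving has its own rule: "if the participant drove a car in the past month, where disability is defined as having not driven".

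Section 3.3 states: "Patients are eligible at any time point during their treatment here at OSU". The calendar in section 8.0 schedules functional assessments at baseline, at weeks 4, 7, 10, 13 and 24, and at treatment visits.

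**The concern.** There are two problems.

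- **The time rule.** Passing once anywhere in the window is enough, and nothing requires the criterion to hold at 3 or 6 months or to last. A patient who passes at week 4 and then declines permanently would sit in the resilient group, against the idea in section 2.2 of recovering function after a health event.
- **The time origin.** The window runs from diagnosis and the emphasised times from treatment start, but study scores exist only from enrolment, which may come much later than either.

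At stake are the comparisons of resiliency with clinical factors and, through the shared window, the change-point analysis. Section 6.2 also says that the functional status comparison will inform a larger trial, so a label that does not mean what it says could carry over.

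**Working it through.** The plan gives no expected rate, sample size or power for resiliency, so there is no figure to reproduce.

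**1. One early pass is enough**

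Inputs: item scores 0 to 2 on 16 activities (section 4.6), visits at weeks 4, 7, 10, 13 and 24 (section 8.0), and the 50% threshold (section 6.2). Assumptions: a maximum total of 32, function F = 32 - score, and an invented course starting from a baseline score of 4.

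Baseline F = 32 - 4 = 28, so a pass needs F of at least 0.5 x 28 = 14, that is, a score of 18 or less.

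| Week | Score | F | F / 28 | Pass |
|---|---|---|---|---|
| 4 | 6 | 26 | 93% | yes |
| 7 | 10 | 22 | 79% | yes |
| 10 | 16 | 16 | 57% | yes |
| 13 | 24 | 8 | 29% | no |
| 24 | 32 | 0 | 0% | no |

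The any-visit rule gives resilient. Classification at week 13 or week 24 gives not resilient.

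**2. Does this depend on the conversion?**

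- Maximum 31 (driving scored 0 or 1, last score 31): baseline F = 27, and the ratios are 25/27 = 93%, 21/27 = 78%, 15/27 = 56%, 7/27 = 26% and 0%. The pattern is the same.
- Number of the 16 activities done without help: section 4.6 says "disability is defined as the need for personal assistance or inability to perform the activity". A score of 4 means 2 to 4 activities disabled, so 12 to 14 intact and 6 to 7 needed. A score of 6 leaves 10 to 13 (pass). A score of 24 leaves 0 to 4 (fail). A score of 32 leaves 0 (fail).

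So week 4 passes and weeks 13 and 24 fail each time. The exact maximum still matters at the boundary: a move from 4 to 18 gives 14/28 = 50% (pass) with a maximum of 32, but 13/27 = 48% (fail) with 31.

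**3. Direction and size**

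Everyone who passes at week 13 also passes at some visit, so the any-visit proportion among patients scored at week 13 cannot be smaller than the week-13 proportion. Section 6.1 plans 30 enrolled and projects 20. One patient reclassified moves the proportion by 1/20 = 5.0 points or 1/30 = 3.3 points.

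**4. Time anchors**

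Let T be months from treatment start to enrolment. The emphasised times fall 3 - T and 6 - T months after the study baseline. The first is negative when T exceeds 3, and both are negative when T exceeds 6. A patient enrolled more than 12 months after diagnosis has no study score in the window. The footnote to Table 2 in section 4.12 provides for patients already on treatment at visit 1, so late enrolment is expected. For such patients the change point anticipated at treatment start also precedes the first study score.

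The calendar visits fall close to the emphasised intervals if timed from enrolment: 13 x 7 / 30.44 = 3.0 months and 24 x 7 / 30.44 = 5.5 months.

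**The case against.** The best counter-argument is that mixed models imply repeated measurements. On that view resiliency is judged visit by visit, *at any point* means at any assessment, and the 3- and 6-month emphasis marks the times that matter. The word *maintain* also sits badly with calling a steady decline resilient. This reading is possible, but section 6.2 does not state it, and the chi-square and t or Wilcoxon comparisons still need either one class per patient or a named visit.

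A reader might go further and infer that resiliency cannot be scored, or that the compared groups must overlap because *worsening* has no threshold. The documents do not support that. Section 4.6 equates a higher score with lower function, so a reversed score is the natural conversion, and the contrast most naturally means resilient against not resilient. Appendix G, the survey form, is not in the text reviewed and may hold a scoring note. These are details to state, not evidence of an unworkable endpoint.

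It is also fair that the worked course is invented and extreme. On the reversed score, a patient starting at 4 fails only above 18, so few may change class. Section 3.3 says that patients are approached at their initial visit, so many may enrol early. Both points limit the likely size; neither repairs the rule.

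**Conclusion.** The concern holds in a limited form. As a patient-level label, the rule lets one early passing visit outweigh later lasting loss, and its time anchors can fall outside the period in which the study measures function. The conclusion on timing follows from the text. The percentages rest on an assumed score course and assumed totals of 31 or 32. How many patients would change class, and how many will enrol late, is unknown.

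Two further inferences should be avoided. The finding does not weaken the primary feasibility endpoint or the power statement in section 6.2.1, because neither uses resiliency. Nor is the change-point analysis spared because it models scores rather than the label: it is set over the same year from diagnosis. This is a secondary endpoint in a small pilot, worth correcting before analysis because the correction is cheap.

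**What to change.** Delete *at any point* in section 6.2 and use fixed visits already in the calendar. Suggested text:

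*Resiliency will be classified at Visit 5 (week 13, principal) and Visit 6 (week 24), timed from enrolment. Function F is [stated maximum] minus the total score on [named instrument], with the scoring of the driving item stated. A patient is resilient at a visit if F is at least 50% of F at Visit 1; [handling of a Visit 1 F of 0]. All other patients with a score at that visit form the comparison group. Deaths and missing scores will be counted and reported separately.*

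Use these groups in the chi-square, t or Wilcoxon and GLMM comparisons in place of *worsening functional status*. If Appendix G already gives the conversion, refer to it. The 16-item survey is the safer instrument: a note under the assessment table in section 4.3 may mean that the EQ-5D-5L has no baseline value. Re-anchor the change-point window to enrolment, or state how late enrollees are handled.

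The cost is a short rewrite and no new data; the sponsor's 50% threshold is unchanged. There are downsides. Fewer patients will be classed as resilient. Recovery seen only between the fixed visits is not counted. The anchor moves from treatment start to enrolment. Each comparison covers only survivors with a score at that visit, a real selection in advanced lung cancer, which is why deaths and missing scores need their own line.

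### Section 6.2 defines resiliency and the change point over 12 months from diagnosis, but dated functional scores run only from Visit 1 to week 24 and patients may enrol already on treatment

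*Combined protocol and SAP*

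**What the plan says.** Section 6.2 (Secondary Endpoints) works from two time origins. Resiliency is keeping or regaining at least half of baseline function "at any point during the 12 months after diagnosis with specific emphasis at 3 and 6-months post- the start of treatment". The segmented mixed model is meant to locate when patients' "functional status scores change during the 12-months post-diagnosis", and the section adds: "We anticipate that the start of treatment will be a change point depending on treatment tolerability vs. toxicity". Clinical factors are then compared "between participants demonstrating resiliency vs. worsening functional status" by chi-square, t or rank-sum tests, and GLMMs test for differences in resiliency, adjusted for clinical and demographic variables that are not listed. The same section also refers to a shorter period: "we will compare functional status in the 24-week follow-up period".

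Data collection runs on a third origin, enrolment. Section 6.1 has follow-up continuing to 24 weeks after enrolment. The Study Calendar (Section 8.0) marks functional status at Visit 1, at weeks 4, 7, 10, 13 and 24, and at every treatment visit. Its column reaching to 24 months is marked for survival status alone, and Section 3.1 gives overall survival as the purpose of that longer follow-up. Sections 3.1, 4.1 and 4.6 ask for functional scores every 3 weeks, and Section 4.1 adds triggered assessments. None of them says when these stop.

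Entry is open. Section 3.3 states: "Patients are eligible at any time point during their treatment here at OSU". It also says: "Patients will be approached at their initial visit but we can also offer enrollment at any one of the patients regularly scheduled clinic visits". Section 3.1 describes the cohort as patients "who plan to receive either immunotherapy and or chemotherapy treatment". The footnote to Table 2 (Section 4.12) foresees patients who began treatment before Visit 1 and withholds only the research blood samples from them. No limit is set on time since diagnosis or since treatment start.

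**The concern.** Diagnosis, treatment start and enrolment are three different clocks, and nothing in the plan aligns them. The endpoint is defined on the first two and the scores are collected on the third.

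Two things follow. First, resiliency can be confirmed by what is seen, but its absence cannot be established over a window that is only partly seen. How much is seen depends on when the patient enrolled, so the comparison of resilient with worsening patients may partly reflect enrolment timing. Second, for a patient already on treatment at Visit 1, the baseline is an on-treatment value, while for others it is a pre-treatment value. The plan does not say that the two will be told apart. Section 6.2 also uses these functional data to inform the survey design of a larger trial, so the time axis needs to be interpretable.

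**Working it through.** The plan gives no precision or coverage figure for these endpoints, so there is no stated number to reproduce. The check is calendar arithmetic.

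**Inputs.** The window is 12 months from diagnosis, taken as 52 weeks (Section 6.2). The dated span *s* of functional scores after Visit 1 is 24 weeks on the wording of Section 6.1, or 23 weeks if the calendar is read as week 1 to week 24. Two quantities are not in the documents and are shown as ranges: *d*, weeks from diagnosis to Visit 1, and *x*, weeks from treatment start to Visit 1.

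**Step 1: coverage by dated visits.** Coverage = max(0, min(52, d + s) − d) / 52. With s = 24:

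| d (weeks) | Unseen before Visit 1 | Covered | Unseen after week 24 | Share covered |
|---|---|---|---|---|
| 0 | 0 | 24 | 28 | 24/52 = 46% |
| 13 | 13 | 24 | 15 | 24/52 = 46% |
| 26 | 26 | 24 | 2 | 24/52 = 46% |
| 39 | 39 | 13 | 0 | 13/52 = 25% |
| 52 | 52 | 0 | 0 | 0% |

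With s = 23 the maximum is 23/52 = 44%.

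**Step 2: coverage if the undated scores continued.** Suppose functional scoring went on to 12 months after diagnosis, which the documents do not state. Coverage would be (52 − d)/52: 100%, 75%, 50%, 25% and 0% at d = 0, 13, 26, 39 and 52. Everything still missing lies before Visit 1, and later scoring cannot recover it. For these patients, part of the window has passed before the baseline is even measured.

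**Step 3: the 3- and 6-month landmarks.** The protocol rounds to 12-week quarters. Section 4.1 equates 12 weeks with 3 months. Section 6.1 projects 20 participants surviving 6 months, and Section 6.2.1 describes 20 alive over 24 weeks. On that convention the landmarks fall at study weeks 12 − x and 24 − x.

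- Treatment starts at Visit 1 (x = 0): the landmarks are at study weeks 12 and 24. Both are covered with s = 24. With s = 23 the second is missed by 24 − 23 = 1 week.
- Treatment began more than 12 weeks before Visit 1: the 3-month landmark precedes the first score. Beyond 24 weeks, both do. (Calendar months move these limits to about 13 and 26 weeks.)
- Treatment began at any time before Visit 1 (x > 0): treatment start precedes the first score, so that patient's own data carry no information on a change there.

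**Step 4: effect on classification.** One qualifying score is enough to show the rule was met. Showing that it was not met needs the whole window. Any error therefore runs one way: patients who do not meet the rule while observed may be grouped with the worsening patients although part of their window was unseen. The number depends on the enrolment lags and on recovery outside the observed period, and the documents give neither.

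**The case against.** The strongest reply has five parts.

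- **Scoring may not stop at week 24.** The treatment-visit, 3-weekly and triggered assessments have no stated end. This stands: a reader might infer that no functional score can exist after week 24, and the documents do not go that far. Later scores still cannot fill the period before Visit 1, and triggered scores follow adverse events, so they are not an even substitute.
- **The 6-month landmark.** Taking 6 months as 26 weeks with no tolerance, a reader might infer that no patient can have both a pre-treatment baseline and a 6-month score. The documents do not support this. On their own 24-week convention, a patient starting treatment at Visit 1 has both, or misses the second by about a week.
- **The rule can be met early, and worsening can be seen within 24 weeks.** Both are true and both narrow the problem. But worsening by week 24 does not exclude recovery later in the stated 12 months, and Section 6.2 gives worsening no window of its own.
- **An on-treatment baseline is not in itself wrong.** Section 2.2 counts toxicity and progression among the events from which a patient may recover, and change points are random and estimated, with treatment start only anticipated as one. This stands. The point is that the baselines differ in kind and should be identified.
- **Models are adjusted, and diagnosis date and treatment history are collected (Section 5.4).** Treatment status is not named as a covariate, the simple tests are unadjusted, and adjustment cannot create outcomes that were not observed.

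**Conclusion.** The mismatch is real. As written, the 12-month post-diagnosis window cannot be fully observed from the dated visits for any patient: coverage is at most about 46%, falls to 25% at a 39-week lag, and is nil from 52 weeks. These figures rest on a 52-week year, a dated span of 23 to 24 weeks, and lags that the documents do not give.

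A reader might take the percentages as misclassification rates, or conclude that the non-resilient group is contaminated to a known degree. Neither follows: the size of any misclassification is unknown, and so is the share of patients who will enrol on treatment. Sections 3.1 and 3.3 expect some to be approached before or near treatment start, and those who start treatment at about Visit 1 are largely unaffected at the 3- and 6-month landmarks. The change should be made, but it concerns a secondary endpoint. The primary feasibility decision does not depend on it.

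**What to change.** In Section 6.2:

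- Set time zero at Visit 1. Define the trajectory and resiliency endpoints over the 24-week follow-up period that the section already names, with emphasis at weeks 13 and 24 relative to the Visit 1 score.
- Report results by treatment status at Visit 1 (not started, or already on treatment), or at least describe it, using the treatment history already collected under Section 5.4. With about 20 patients, description may be all the data allow.
- Keep the treatment-start change point and the 3- and 6-month summaries after treatment start as exploratory, in patients with a pre-treatment score, and report the actual time since treatment start.

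It would also help to say in Sections 4.1 and 4.6 and the calendar when the 3-weekly, treatment-visit and triggered functional scores end. That is a small change to protocol text.

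No new data are needed. The cost is a narrower claim: 24 weeks after enrolment in place of 12 months after diagnosis, and the pre-treatment subset may be small. Extending functional scoring would preserve more of the 12-month question, but it adds data collection and still leaves the time before Visit 1 unobserved. The change settles the window only. How half of baseline is computed on a scale where higher scores mean worse function (Section 4.6) remains open.
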